8.4.2 SERIOUS ADVERSE EVENT REPORTING

All SAEs will be reported to the PI within 48 hours after identification and recorded in OncCore by the investigator. All deaths and immediately life-threatening events, whether related or unrelated to the study agent/procedure, will be recorded on the SAE Form and submitted to the PI within 24 hours of site awareness. All SAEs will be followed until satisfactory resolution or until the investigator deems the event to be chronic or the adherence to be stable.

8.4.3 UNANTICIPATED PROBLEM REPORTING

The study investigator will report to the PI unanticipated problems and it will be on the discretion of the PI whether to conduct an evaluation of an unanticipated problem and whether to report it to IRB.

8.4.4 EVENTS OF SPECIAL INTEREST

Not applicable.

8.4.5 REPORTING OF PREGNANCY

Pregnancy when diagnosed will be reported to the PI and to the reviewing IRB as soon as possible, but in no event later than 10 working days after the investigator first learns of the effect.

8.5 SAFETY OVERSIGHT

Serious Adverse Events: Serious Adverse Events (SAEs) from this protocol will be reported concurrently to the IRB (per IRB reporting guidelines) and to the study sponsor via submission through The Online Collaborative Research Environment (OnCore).

Protocol Monitoring Committee (PMC):

The PMC meets monthly and reviews accrual, patterns and frequencies of all adverse events, protocol violations and when applicable, internal audit results.

The data and safety plan will define criteria for stopping the trial according to rules set forth by this protocol. This trial will be continuously monitored by the PI and the research team and reviewed at weekly Head and neck-Endocrine Oncology Research Group meetings. Safety and monitoring reports will be submitted to the PMC after completing the first 2 cycles after the randomization of initial 5 patients in each arm or more frequently if requested by the PMC. A final safety and monitoring report including all 45 patients will be submitted to the PMC within three months of completing the study enrollment. This protocol will be subject to periodic internal audits based on risk or as recommended by the PMC.

9. CLINICAL MONITORING

Data will be captured in OnCore, Moffitt's electronic Clinical Trials Database. For each participant enrolled, the electronic CRF must be completed by the assigned data manager or other authorized study staff. Any paper forms should be typed or filled out indelible ink and must be legible. Errors should be crossed out but not obliterated, the correction inserted, and the change initialed and dated by the investigator or his/her authorized delegate. This also applies to records for those patients who fail to complete the study. If a patient stops dosing or terminates from the study, the dates and reasons must be noted on the CRF. If a patient terminates from the study because of toxicity, thorough efforts should be made to clearly document the outcome. Regulatory documents and case report forms will be monitored internally according to Moffitt Cancer Center Monitoring Policies. Monitoring will be performed regularly by the MCC Clinical Monitoring Core for accuracy, completeness, and source verification of data entry, validation of appropriate informed consent process, reporting of SAEs, and adherence to the protocol, Good Clinical Practice (GCP) guidelines, and applicable regulatory requirements. The investigator should ensure the accuracy, completeness, legibility, and timeliness of the data reported to the Protocol Monitoring Committee.

10. STATISTICAL CONSIDERATIONS

10.1 STATISTICAL AND ANALYTICAL PLANS

This is a randomized phase II clinical trial with 2:1 randomization to adaptive therapy versus conventional therapy. The primary endpoint is time-to-discontinuation (TTD) of treatment, which is a "survival analysis"-type statistical comparison. We plan to enroll 24 patients on the adaptive therapy and 12 on the conventional therapy arm. Assuming uniform enrollment of patients for 2 years, with a minimum follow-up of 2 years, and a one-sided $\alpha = 0.20$, we will have 82% power to detect a hazard ratio of 0.50, assuming 12 and 24 month median TTD for the conventional and adaptive therapy groups. If the median TTD of the adaptive group is 20 months (HR=0.6), the power is 67%.

We anticipate that 20% of the patients will not have the $\geq 50\%$ drop in tumor markers needed for study randomization arm of the study. Thus, we anticipate recruiting ~45 patients to have 36 patients for randomization.

The ~9 patients enrolled to the trial not candidates for the randomization will be given conventional therapy as standard of care. As an exploratory analysis, and realizing that the sample sizes are small, we will compare their PFS rates with the 12 patients from the randomized portion of the trial who receive conventional therapy using the log-rank test.

10.2 STATISTICAL HYPOTHESES

We hypothesize that we will prolong time to treatment discontinuation with the adaptive therapy regimen (**experimental group**) compared to the continuous therapy regimen (**control group**). Literature suggests that the median time to discontinuation with standard (continuous) therapy is 12 months. We hypothesize that the median time to discontinuation will increase to 24 months (Hazard ratio 0.50) with the adaptive therapy regimen. The power of the study to detect this difference is 82% for an alpha of 0.20.

10.3 DESCRIPTION OF STATISTICAL METHODS

10.3.1 ANALYSIS OF THE PRIMARY EFFICACY ENDPOINT(S)

The primary endpoint is the time-to-discontinuation of treatment.

- The measurement endpoint is the status of a patient 12 months following the start of TKI.
- This is a binary metric. 1 = the patients is still receiving TKI at 12 months; 0 = patient is no longer on TKI due to cancer progression and/or toxicity.
- The results will be described as % patients that remain on TKI at 12 months by experimental and control groups.
- The test statistic will a Fisher's Exact test on a two by two contingency table of patient counts based on all four combinations of whether a patient remains or does not remain on TKI (0 or 1) by treatment group (adaptive therapy or continuous therapy)
- We will begin by comparing the historical control patients with the control patients of the trial. If these two groups do not differ (using a Type I error rate of $p > 0.1$) then they shall be combined to provide the patient counts for the Fisher's Exact Test comparison of the control group to the experimental group of the trial.
- If the historical control patients differ from the control patients of the trial (using a Type I error rate of $p < 0.1$) then they will be compared separately to the experimental group using Fisher Exact test's with a Bonferroni adjusted Type I error rate of $p < 0.05$.

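### The primary test in Section 10.3.1 (Fisher's exact test at 12 months with a historical-control pooling step) is not the survival comparison for which 82% and 67% power are stated

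*Combined protocol and SAP*

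**What the plan says.** **Endpoint.** Section 4.2.1 defines the primary endpoint as time to stopping TKI because of progression, intolerability or disease-related death, with a 2-year horizon.

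**Sizing.** Sections 10.1 and 10.4 call TTD a survival-type comparison, with 24 adaptive and 12 conventional patients, two years of uniform accrual, at least two years of follow-up and one-sided alpha 0.20. Section 10.1 states: "we will have 82% power to detect a hazard ratio of 0.50, assuming 12 and 24 month median TTD". It gives 67% if the adaptive median is 20 months (hazard ratio 0.6). Section 10.2 repeats the claim without sidedness: "The power of the study to detect this difference is 82% for an alpha of 0.20". Section 10.4 counts elective withdrawal as an event, with a sensitivity analysis that censors it.

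**Primary analysis.** Section 10.3.1 names the same endpoint and then says "The measurement endpoint is the status of a patient 12 months following the start of TKI". The test is Fisher's "Exact test on a two by two contingency table of patient counts based on all four combinations" of on-TKI status and arm. Code 1 is still receiving TKI. The other code is "0 = patient is no longer on TKI due to cancer progression and/or toxicity".

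**Historical controls.** The order of work is fixed: "We will begin by comparing the historical control patients with the control patients of the trial". If p > 0.1, "then they shall be combined to provide the patient counts for the" Fisher comparison with the adaptive arm. If p < 0.1, each control group is compared separately with the adaptive arm "with a Bonferroni adjusted Type I error rate of" p < 0.05.

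No log-rank or Cox analysis of TTD is specified anywhere. The only log-rank test is the exploratory progression-free survival comparison in Section 10.1.

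**The concern.** The sample size is justified for one test, and the section headed as the primary efficacy analysis prescribes another. They differ in time point (12 months against a time-to-event measure with a 2-year horizon), in method, in control group and in error rate. Section 10.3.1 gives no sidedness, no alpha for the pooled test, and no number or source for the historical controls. A reader cannot tell what error rate a positive result would carry, and these choices could be made after the data are seen.

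The pooling rule raises a second issue. With 12 trial controls, a test at the 0.1 level has little ability to detect that the historical patients fared differently, so a biased historical rate would usually be absorbed into the control group.

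The 0/1 coding also does not match the rest of the plan. It has no place for elective withdrawal, an event under Section 10.4. It gives no code to an adaptive-arm patient in a planned off-TKI interval at month 12, a state that Section 7.3.3 expects to occur.

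**Working it through.** **Inputs from Sections 10.1 and 10.4.** n = 24 and 12; medians 24 (or 20) and 12 months; accrual A = 24 months; minimum follow-up F = 24 months; one-sided alpha 0.20. *Assumption:* exponential TTD.

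**1. Reproduce the stated power as a survival test.** With λ = ln 2 / median, the event probability is 1 − [exp(−λF) − exp(−λ(F+A))]/(λA).

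- Control: 0.865, so 12 × 0.865 = 10.38 events.
- Adaptive, median 24: 0.639, so 15.34 events.
- Adaptive, median 20: 0.704, so 16.91 events.

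Power = Φ(|ln HR| / √(1/d0 + 1/d1) − 0.842).

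- HR 0.5: 0.693/0.402 − 0.842 = 0.883, power 81.1%.
- HR 0.6: 0.511/0.394 − 0.842 = 0.454, power 67.5%.

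Log-rank simulation gives 81% and 68%. The stated 82% and 67% are therefore sound for a one-sided log-rank test. Two-sided 0.20 gives 67% and 51% by the same formula and does not fit.

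**2. Same assumptions, binary outcome at 12 months.** The proportion on treatment is 0.5^(12/median): 0.500 control, 0.707 (HR 0.5), 0.660 (HR 0.6). Exact enumeration of one-sided Fisher at 0.20, 24 versus 12, gives 52% and 40%, with an actual size of 10.4%. This is an illustration only, because 10.3.1 never tests the randomised patients alone at 0.20.

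**3. The whole 10.3.1 procedure.** *Assumptions:* 12, 30, 100 or 200 historical controls; two-sided Fisher pre-test at 0.1; one-sided 0.05 for the separate comparisons; trial control rate 50%. With the historical rate also 50%:

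| Pooled alpha (one-sided) | Rule when not pooled | Power, HR 0.5 | False-positive rate |
|---|---|---|---|
| 0.20 | trial-control test decides | 65-80% | 14-15% |
| 0.20 | either test may reject | 68-82% | 14-16% |
| 0.10 | either test may reject | 47-70% | 6.5-8% |
| 0.05 | trial-control test decides | 33-54% | 3-4% |

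Each range runs over the four assumed historical sample sizes.

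**4. Unequal historical rate, pooled alpha 0.20.**

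- Historical rate 40%: pooling occurs in 86-91% of trials. The false-positive rate is 23-38% if the trial-control test decides and 26-40% if either may reject.
- Historical rate 60%, trial-control test deciding: power at HR 0.5 is 51-55% and the false-positive rate 4-9%.

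**5. Survival test with observation stopped at 24 months.** Expected events at HR 0.5 are 12 × 0.75 = 9.0 and 24 × 0.50 = 12.0, so power is 76.7%. At HR 0.6 they are 9.0 and 13.55, so power is 63.5%. Simulations with a cap at 24 months, or at 22 months (assuming randomisation two months after TKI start), with and without stratification (assuming one third MTC), give 75-77% and 62-64%.

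**The case against.** Four replies deserve weight.

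*Historical controls may restore the power.* With 200 of them at the same true rate, pooled alpha 0.20 and either separate test allowed to reject, power is 82.4% (HR 0.5) and 67.5% (HR 0.6), which matches the stated figures. A reader might infer from step 2 that 10.3.1 is underpowered; that is not shown. The match does not show that the sponsor calculated power this way either, since the sizing text counts only 24 and 12 randomised patients. What stands is that the power of 10.3.1 is unstated and depends on inputs the documents omit.

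*Bonferroni implies a decision rule.* Two comparisons at an adjusted 0.05 ordinarily mean a familywise 0.10 with either able to reject. It would be too strong to say the plan has no rule when the two disagree. The rule is implied and should be written down.

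*Planned pauses need not count against the adaptive arm.* A reader might infer that the coding erases that arm's expected advantage. The text does not support this: code 0 requires progression or toxicity, and note a to Table 8 lets the cycle count run on through a pause. This is a gap in the coding, not a demonstrated bias. Likewise, most disease-related deaths would probably fall under progression.

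*There are not two rival primary tests.* Correct: one test is specified, alongside a power statement that belongs to another.

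**Conclusion.** The plan is wrong as written and should be corrected before analysis. The test in 10.3.1 is not the comparison on which the trial was sized, and the 82% and 67% cannot be carried over to it. They are not arithmetic errors: they hold for a one-sided log-rank test of TTD with follow-up past month 24. For 10.3.1 itself, the supportable statement is that power and error rate are undetermined. The illustrative 33-82% rests on exponential TTD, equal control rates, 12-200 historical controls, and assumed alphas and decision rules.

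The weakness of the pooling rule is shown for the case examined. A 10-point difference in control rates passes the pre-test in about 86-91% of trials and, with the pooled test at one-sided 0.20, gives a false-positive rate of about 23-40%. The documents do not say that the historical rate differs, so this measures exposure and is not a prediction.

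The coding conflict with Section 10.4 on withdrawal, and the missing code for planned off-TKI intervals, follow directly from the text.

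**What to change.** In 10.3.1, replace the Fisher test and the historical-control rule with one primary analysis: a log-rank test of TTD in all randomised patients, concurrent controls only, one-sided alpha 0.20, preferably stratified by DTC/MTC to match the randomisation, with a Cox hazard ratio and confidence interval.

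- Use the events in 4.2.1, and the withdrawal rule and sensitivity analysis in 10.4.
- State in the endpoint definition that a planned off-TKI interval in the adaptive arm is not a discontinuation event.
- Make the 12-month proportion and any historical comparison descriptive.
- State one time origin (10.3.1 counts from TKI start, while randomisation can come as late as Cycle 3 Day 1) and one data cut-off. Sections 6.1.8 and 7.3.3 place treatment after 24 months outside the protocol. If TTD is censored there, restate power as about 75-77% (HR 0.5) and 62-64% (HR 0.6).

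If the sponsor prefers to keep the 12-month Fisher test, it should give that test's sidedness, alpha, coding, decision rule and power, and the number and source of the historical controls.

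The cost is a protocol amendment, which Section 13.2 sends to the IRB, and a stated power that may fall below 80%. No extra visits or procedures follow, and no extra patients provided the sponsor accepts the lower power.

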4. STUDY DESIGN AND ENDPOINTS

4.1 DESCRIPTION OF THE STUDY DESIGN

This is a pilot randomized phase 2 clinical trial to evaluate the efficacy and tolerability of TKI therapy through adaptive (intermittent) versus conventional (continuous) regimen in patients with DTC or MTC. Eligible subjects with DTC or MTC will have measurable disease according to Response Evaluation Criteria in Solid Tumors (RECIST 1.1) and will be randomized 2 to 1 to receive adaptive (intermittent) versus conventional (continuous) therapy when and if the tumor marker drops 50% or more from the baseline level (before initiating TKI treatment) within the first two months of treatment. Randomization will be stratified by cancer types, DTC vs. MTC. Patients in which the tumor marker does not drop by 50% or more within 2 months (“non-responders”) will be kept on conventional therapy and used to compare with the patients who drop their tumor markers by 50% or more as an exploratory analysis.

All patients will start receiving standard of care treatments: Lenvatinib 24 mg daily or Sorafenib 400 mg twice daily with DTC; Cabozantinib 140 mg daily or Vandetanib 300 mg daily with MTC. Doses will be adjusted as needed due to toxicity or drug tolerance in both arms (See section 6.1.8).

- Patients in the conventional therapy regimen (“responders” and non-responders”) will receive continuous (daily) treatment at the indicated dose.

- Patients in the adaptive therapy regimen will receive TKI therapy in cycles: continuous (daily) treatment at the indicated dose until the patients’ tumor marker (thyroglobulin in DTC patients; calcitonin or CEA in MTC patients) drops by $\geq 50\%$ from the level at the time of enrollment (“baseline” level). $\geq 70\%$ of Only tumor markers that meet inclusion criteria at baseline can be used for randomization and adaptive therapy purposes. A new cycle of TKI treatment will begin:

1. When/if the tumor marker increases to $\geq 70\%$ of the “baseline” level.
OR
2. At the discretion of the treating physician, if a patient develops worsening disease-related symptoms with rising tumor marker levels indicating disease progression. In the case of resumption for disease-related symptoms, TKI treatment will continue until the symptoms improve at the discretion of the treating physician and the tumor markers are again $\leq 50\%$ from the level at the time of enrollment.

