7.3.3 FOLLOW-UP

Follow-up Visits

Study participants will be seen weekly for the first cycle (Cycle 1 Days 8, 15 and 22), every two weeks for the second cycle (Cycle 2 Days 1, 15), every four weeks until cycle 12 (Day 1 of Cycles 3-12); and every 2 cycles thereafter until end of study (Day 1 of cycles 14, 16, 18, 20 and 24). However, when the patient is off the TKI with observation only in the adaptive arm, the patient needs to follow up every 28 days (+/- 7 days) for determination of starting a new cycle.

In each scheduled visit we will:

- Obtain vital signs.
- Record all concomitant medication use.
- Perform a comprehensive physical examination.
- Evaluate ECOG performance status.
- Obtain laboratory tests and urinary dipstick.
- Assess for AEs and SAEs.
- Assess compliance with the medication.
- Assess survival.

Thyroid panel evaluation

Thyroid panel will be assessed every 2 weeks during the first two cycles (Cycle 1 Day 15, Cycle 2 Day 1, Cycle 2 Day 15, and Cycle 3 Day 1). If the tumor marker (thyroglobulin in DTC patients; calcitonin or CEA in MTC patients) drops by $\geq 50\%$ from baseline (Cycle 1 Day 1) during the first two cycles (analysis of Cycle 3 Day 1 included), the patient will be randomized to receive either standard (continuous) or adaptive (intermittent) therapy. Patients randomized to

the standard therapy arm will then get Thyroid panel checked every 3 cycles (Day 1 of Cycle 6, 9, 12). Patients randomized to the adaptive therapy arm will get Thyroid panel checked every cycle (Day 1) during the first two years. After 24 months, patients in the adaptive therapy regimen who remain on TKI therapy will be given the choice to continue with the adaptive therapy regimen and monitoring of the thyroid panel in every cycle; or to convert to standard (continuous) regimen in which case thyroid panel evaluation will be checked every 3 cycles. In either case, all patients that continue to receive TKI therapy beyond 24 months will be treated off trial. Patients in which the tumor marker does not drop $\geq 50\%$ within the first two months of TKI therapy will be managed by the standard of care.

Diagnostic imaging

Diagnostic imaging of affected and suspected sites (CT and/or MRI) will be done at Day 1 of cycles 3, 6, 9, 12, 16, 20, 24 in all patients. Diagnostic imaging will continue to be done every 4 months thereafter while the patient remains on TKI therapy or as clinically indicated otherwise.

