10.4 SAMPLE SIZE

The planned study is a randomized clinical trial, with 2:1 randomization to adaptive therapy versus conventional therapy. The primary endpoint is time-to-discontinuation (TTD) of treatment, which is a “survival analysis”-type statistical comparison. We plan to enroll 24 patients on the adaptive therapy and 12 on the conventional therapy arm. Assuming uniform enrollment of patients for 2 years, with a minimum follow-up of 2 years, and a one-sided $\alpha = 0.20$, we will have 82% power to detect a hazard ratio of 0.50, assuming 12 and 24 month median TTD for the conventional and adaptive therapy groups. If the median TTD of the adaptive group is 20 months (HR=0.6), the power is 67%.

We anticipate that 20% of the patients will not have the $\geq 50\%$ drop in tumor markers needed for study randomization arm of the study. Thus, we anticipate recruiting ~45 patients to have 36 patients for randomization.

Objective time-to-discontinuation criteria are described in Section 4.2.1. Patients may electively withdraw from treatment at any time and will be counted as a discontinuation event. All randomized patients will be included in the primary analysis. A sensitivity analysis will also be conducted, where the patients who choose to withdraw are considered as censored (non-events) at the time of withdrawal.

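### The 12-month status clock starts at TKI start, not at randomization: a slight dilution of the randomized contrast, and a possible bias if historical controls without the same landmark are pooled

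*Combined protocol and SAP*

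**What the plan says.** Section 10.3.1 names time to discontinuation as the primary endpoint and then reduces it to a yes/no status: "The measurement endpoint is the status of a patient 12 months following the start of TKI". The arms are compared by Fisher's exact test.

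Randomization comes later than TKI start. Section 4.1 randomizes patients "when and if the tumor marker drops 50% or more from the baseline level (before initiating TKI treatment) within the first two months of treatment". Section 7.3.3 sets the checks: "Thyroid panel will be assessed every 2 weeks during the first two cycles (Cycle 1 Day 15", then Cycle 2 Day 1, Cycle 2 Day 15 and Cycle 3 Day 1. Its rule for a qualifying drop reads "analysis of Cycle 3 Day 1 included), the patient will be randomized to receive either standard (continuous) or adaptive (intermittent) therapy". Section 10.4 adds "All randomized patients will be included in the primary analysis", and section 10.1 gives the arm sizes: "We plan to enroll 24 patients on the adaptive therapy and 12 on the conventional therapy arm".

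Section 10.3.1 also brings in an external group: "We will begin by comparing the historical control patients with the control patients of the trial". The two control groups are combined if they do not differ at a 0.1 threshold. This is the only section that mentions historical controls. It gives no number, selection rule, response requirement or time origin for them. No section resets the clock or sets a landmark.

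**The concern.** A patient who reaches randomization has, in effect, already come through the first 0.5 to 2 months of the 12-month window without discontinuing. The documents do not say in words that the patient must still be on TKI, but the randomization rule implies it. During that time both arms receive the same treatment, so it can add nothing to the contrast, yet it raises the on-treatment percentage in both arms.

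Two things are at stake. Within the trial, part of the window carries no information on the regimen. Against historical controls, a group that had to survive the lead time may be compared or pooled with one that did not. With only 12 randomized controls, a larger historical group could dominate the pooled control arm.

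**Working it through.** **Inputs from the documents.** 24 adaptive and 12 conventional patients, one-sided alpha 0.20, medians 12 and 24 months, 2 years of uniform accrual, at least 2 years of follow-up (10.1). First qualifying check at Cycle 1 Day 15 (14 days, about 0.5 month); last at Cycle 3 Day 1 (56 days, about 1.8 months), described in 4.1 as two months.

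**Assumptions.** Exponential times with those medians applying from TKI start; an event-free lead of L months, 0.5 to 2; for the last two steps, 12 to 100 historical controls and a nominal one-sided 0.20. Section 10.3.1 states no level for the pooled test, so 0.20 is taken from 10.1.

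**Step 1: the plan's own figure.** A log hazard ratio calculation with 25.7 expected events gives 81.1% power for a hazard ratio of 0.50, and a simulated log-rank test (20,000 runs) also gives 81.1%. The stated 82% is reproduced. It belongs to a time-to-event test, not to the 12-month Fisher test.

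**Step 2: the randomized arms.** The on-TKI rate at 12 months from TKI start, given an event-free lead, is 2^(-(12 - L)/median). Power is from exact enumeration of Fisher's test, 24 vs 12, one-sided 0.20.

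| Lead L (months) | Conventional | Adaptive | Difference (points) | Power |
|---|---|---|---|---|
| 0 (clock at randomization) | 50.0% | 70.7% | 20.7 | 52.1% |
| 0.5 | 51.5% | 71.7% | 20.3 | 51.5% |
| 1 | 53.0% | 72.8% | 19.8 | 50.9% |
| 2 | 56.1% | 74.9% | 18.8 | 49.3% |

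At L = 2, for example, 2^(-10/12) = 0.561 and 2^(-10/24) = 0.749. The loss is 0.4 to 1.9 points of difference and 0.6 to 2.8 points of power.

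**Step 3: historical controls, if unselected and counted from TKI start.** With a 12-month median their 12-month rate is 50.0%. By month 2, 1 - 2^(-2/12) = 10.9% of them are already off TKI (2.8% by month 0.5). With no adaptive effect, both trial arms stand at 56.1% when L = 2, which is 56.1 - 50.0 = 6.1 points higher from the lead alone.

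**Step 4: the pooling test.** At L = 2 the 0.1 gate finds a difference in only 7% to 9% of trials, against 5% to 8% with no lead, so it offers little protection. The error rates below are for a trial with no adaptive effect in which the gate has allowed pooling.

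| Historical controls | Error, L = 0 | L = 1 | L = 2 |
|---|---|---|---|
| 12 | 15.7% | 18.2% | 21.1% |
| 24 | 13.5% | 17.0% | 21.3% |
| 50 | 14.5% | 19.5% | 25.8% |
| 100 | 14.3% | 20.3% | 28.1% |

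At L = 1 the error stays at or near the nominal 20%. It clearly exceeds 20% only with a lead near 2 months and the larger historical groups.

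**The case against.** **The randomized effect is very small.** One patient is 1/12 = 8.3 points in the conventional arm and 1/24 = 4.2 points in the adaptive arm, so a loss of at most 1.9 points is less than half a patient. This stands. A reader might infer that guaranteed time before randomization biases the comparison of the arms. It does not: the lead precedes assignment and is the same in expectation in both arms, so type I error in that comparison is not inflated.

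**The historical-control bias is not demonstrated.** A reader might take it as a fact that the trial is favoured over historical controls. The documents do not support that. The group is undefined, and if it shares the responder condition and landmark, steps 3 and 4 reduce to zero. What stands is that the plan permits the bias and has no safeguard against it.

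**The origin of the medians is not stated.** If the 12-month median is counted from TKI start in randomized patients, the control rate is 50% by definition. A hazard ratio of 0.50 after randomization then gives 0.5^0.5 = 70.7%, so the 20.7-point contrast is intact. On that reading, 12 months from randomization with L = 2 would give 2^(-12/20) - 2^(-12/10) = 66.0% - 43.5% = 22.4 points (before rounding). The later clock still yields slightly more contrast, though partly because it follows patients longer after randomization.

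**A larger conflict comes first.** Section 4.2.1 defines time to discontinuation at 2 years and 10.1 powers a survival comparison, while 10.3.1 tests a 12-month proportion with about 52% power even with the clock at randomization. That is a separate and bigger problem. If it is resolved in favour of a time-to-event test, the 12-month percentages here fall away, but the origin must still be stated.

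**PFS and OS.** A reader might extend the criticism to both. Section 10.3.2 gives no origin for either, so no error is shown there.

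**Conclusion.** The point holds as a modest one. The clock in 10.3.1 starts before randomization and includes 0.5 to 2 months that cannot separate the arms. The randomized comparison is slightly diluted and not biased: 18.8 to 20.3 points against 20.7, and at most about 3 points of Fisher power, under constant hazards with medians applying from TKI start.

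The more serious consequence is conditional. If the historical controls are unselected and counted from TKI start, the trial arms look up to about 6 points better from the lead alone, and pooling could take the one-sided error from about 14-16% to 21-28%. Those upper figures assume that every patient has a 2-month lead and that there are 12 to 100 historical controls. The documents neither confirm nor exclude that situation.

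**What to change.** - **Randomized arms.** Measure time to discontinuation and any 12-month status from randomization. This is a wording change. Section 4.1 follows everyone for at least 24 months from treatment initiation, and 12 months from randomization falls at month 14 at the latest (12 + 2), so no follow-up is added. Assignments are made through a web system (10.5.1), so the date should be available.
- **Historical controls.** State who they are, how many, and when their clock starts. Use them in the primary test only if the same marker-response condition and landmark can be applied; otherwise base the primary test on the randomized arms alone. This is more than wording. The trial checks markers every two weeks in the first two cycles (7.3.3), and 7.1.1 lists the frequency of thyroglobulin monitoring as outside standard care. Historical records may lack the values needed, and those controls may then be lost from the primary test.
- **Exploratory PFS comparison in 10.1.** Use a common landmark for the non-responders and the randomized conventional patients, for example the end of the response window at Cycle 3 Day 1.
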